8.1. Primary Outcome and Methodology

Efficacy will be assessed by the evaluation of the mean change from baseline in DAS28-hsCRP, ACR response, count of tender/painful and swollen joints, global assessment of disease activity, subject assessment of arthritis pain, and HAQ-DI at the specified time points.

8.1.1. DAS28-hsCRP

The DAS28 is a measure of disease activity in 28 joints and the core set of variables (individual components) for DAS28 for this study include:

- Number of tender joints with a total of 28 joints assessed for tenderness (TJC28)
- Number of swollen joints with a total of 28 joints assessed for swelling (SJC28)
- Subject global assessment for disease activity using VAS (PtGA)
- hsCRP (mg/L)

See details of the individual components in [Section 8.1.3](#), [Section 8.1.5](#) and [Section 1.7](#).

Unless otherwise specified, the DAS28-hsCRP mentioned in this document is based on 3 individual components (TJC28, SJC28 and hsCRP) and calculated using the following equation:

$$\text{DAS28-hsCRP(3)} = [0.56\sqrt{\text{TJC28}} + 0.28\sqrt{\text{SJC28}} + 0.36 \ln(\text{hsCRP} + 1)] \times 1.10 + 1.15,$$

where hsCRP must be in a unit of mg/L. High DAS28-hsCRP value indicates more severe disease activity.

Regarding 4-component DAS28-hsCRP analyzed in the sensitivity analysis, it is calculated using the following equation, consisting of 4 individual components (TJC28, SJC28, hsCRP and subject global assessment of disease activity):

$$\text{DAS28-hsCRP(4)} = 0.56\sqrt{\text{TJC28}} + 0.28\sqrt{\text{SJC28}} + 0.36 \ln(\text{hsCRP} + 1) + 0.014 \times \text{PtGA} + 0.96,$$

where hsCRP must be in a unit of mg/L and PtGA is in a scale of 0 - 100 mm where 0 represents very well and 100 represents not well.

8.1.3. Tender/Swollen Joints Count

Each of the 68 joints will be evaluated for tenderness and 66 joints will be evaluated for swelling (hips are excluded for swelling) prior to randomization at Visit 1 and at each subsequent visit as indicated in the Schedule of Events. Each individual joint is to be examined and assessed as tender or not tender and as swollen or not swollen.

Individual joint with missing assessment will not be imputed. If a joint was replaced prior to the first dose of study drug, the joint will be considered as non-evaluable at baseline and all subsequent post-baseline visits. If the joint replacement was occurred after first dose, the joint will be counted as both tender joint and swollen joint at all subsequent visits after joint replacement. The number of tender and swollen joints will be calculated by summing all joints. If there are non-evaluable or missing joints among the 68/66 joints at a given visit, the prorated tender and swollen joints count (TJC68 and SJC66) will be calculated using the following formula. If less than half of the joints are assessed at that visit, the TJC68 and SJC66 will be treated as missing.

$$\text{TJC68} = 68 \times \frac{\text{total number of tender joints}}{68 - (\text{number of nonevaluable or missing joints out of 68 joints})}$$

$$\text{SJC66} = 66 \times \frac{\text{total number of swollen joints}}{66 - (\text{number of nonevaluable or missing joints out of 66 joints})}$$

As for the scores considering 28 joints for both tenderness and swelling, denoted as TJC28 and SJC28 respectively, the following subset will be assessed (both right and left side):

- Shoulder

- Elbow
- Wrist
- Metacarpophalangeal (MCP) I, II, III, IV, and V
- Thumb interphalangeal
- Proximal interphalangeal (PIP) II, III, IV, and V
- Knee

If at least half of the joints are assessed at a given visit, the similar prorated tender and swollen joints count (TJC28 and SJC28) will be calculated as follows:

$$TJC28 = 28 \times \frac{\text{total number of tender joints}}{28 - (\text{number of nonevaluable or missing joints out of 28 joints})}$$

$$SJC28 = 28 \times \frac{\text{total number of swollen joints}}{28 - (\text{number of nonevaluable or missing joints out of 28 joints})}$$

If less than half of the joints are assessed at that visit, the TJC28 and SJC28 will be treated as missing.

8.1.4. Subject Assessment of Arthritis Pain (VAS)

Per protocol version 3.0 (dated 08Feb2019), the subject is asked to measure his/her arthritis pain by marking a vertical tick on a 100mm horizontal line, where left end (0 mm) represents extreme pain and the right end (100 mm) represents no pain. Starting from protocol version 4.0 (dated 03Apr2020), the subject will be asked to measure his/her arthritis pain by marking a vertical tick on a 100mm horizontal line, where the left end (0 mm) represents no pain and the right end (100 mm) represents extreme pain. The visit and visit date when the subject started or switched to the correct scale described in protocol version 4.0 will be captured in eCRF page Corrected VAS Pain Scale.

Due to the VAS scale was reversed from the standard way they are presented in the clinical trial during protocol version 3.0 (dated 08Feb2019), scoring of the VAS scale was found to be variable across the sites. The clinical team will determine on a subject by subject basis how the subject assessment of arthritis pain was scored and identify subjects who completed consistently the subject assessment of arthritis pain throughout the study to be included in the relevant sensitivity analyses. The detail of subjects who will be included for the relevant sensitivity analyses will be provided in a separate document and will be reviewed and finalized by sponsor prior to the final database lock.

The arthritis pain scores to be used in the analysis will be the length from the anchor of no pain to the vertical tick marked by the subject, which is the number reported on eCRF using the correct scale and the value of 100 minus the number reported using the reversed scale.

8.1.5. Physician and Subject Global Assessment of Disease Activity (VAS)

Physician and subject global assessment of disease activity is measured by both the physician and the subject indicating the subject's current disease status by marking a vertical tick on a 100mm horizontal line, where the left end (0 mm) represents not well and the right end (100 mm) represents very well.

Due to the VAS scale was reversed from the standard way they are presented in the clinical trial during protocol version 3.0 (dated 08Feb2019), scoring of the VAS scale was found to be variable across the sites. The clinical team will determine on a subject by subject basis how the physician and subject global assessment of disease activity was scored and identify subjects whose physician and subject global assessment of disease activity was completed consistently thought the study to be included in the relevant sensitivity analyses. The detail of subjects who will be included for the relevant sensitivity analyses will be provided in a separate document and will be reviewed and finalized by sponsor prior to the final database lock.

The physician and subject global assessment score to be used in the analysis will be the length from the anchor of very well to the vertical tick marked by the physician and subject, namely the value of 100 minus the number reported on eCRF page.

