6.3.1 Disease Activity Score Using 28 Joint Counts

Disease activity score using 28 joint counts (hsCRP) will be evaluated prior to randomization at Visit 1 and at each subsequent visit.

The core set of variables for DAS28 for this study include:

- Number of tender and swollen joints with a total of 28 joints assessed for tenderness and 28 for swelling (Appendix 13.5)
- Subject's global assessment of disease activity (VAS) (Appendix 13.8)
- hsCRP

Note: During the Protocol Amendment 2 dated 08 Feb 2019, the subject's global assessment of disease activity VAS scale was reversed from the standard way they are presented in clinical trials. Scoring of this VAS scale was found to be variable across the sites, since some sites used the reverse scales, while others used the original anchors. Given this inherent

variability, the primary endpoint will now include only the 3 component DAS28-hsCRP, excluding the global assessment of disease activity VAS.

DAS28 based on CRP (DAS28-CRP) may be calculated using 3 or 4 variables.

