DAS28-CRP(4) is computed using 4 variables: swollen and tender joint count, CRP, and subject's global assessment of disease activity. DAS28-CRP(3) only includes swollen and tender joint count and CRP as subject global assessment has been excluded. DAS28-CRP(3) may seem more feasible than DAS28-CRP(4) as it does not include subject global assessment, therefore it may be less influenced by subject's mood, etc., and may be considered a more reliable measure of disease activity. Baseline and 4 months disease activity data from 239 rheumatoid arthritis patients treated with a biological agent were extracted from the Danish registry for biological treatment in rheumatology (DANBIO). DAS28-CRP(4) at baseline was 4.8 ± 1.2 versus 4.6 ± 1.1 for DAS28-CRP(3). After 4 months of biological treatment, the scores for DAS28-CRP(4) and DAS28-CRP(3) had improved by -1.39 ± 1.34 ($p < 0.0001$) and -1.18 ± 1.22 ($p < 0.0001$), respectively. It was concluded that the thresholds for low and high disease activity and for improvements were the same for the 2 scores. While DAS28-CRP(3) yielded lower scores, categorized less patients as having high disease activity level, and scores may differ in individual subjects, and was less sensitive to change than DAS28-CRP, the 2 DAS-scores were highly correlated at both baseline ($r = 0.96$, $p < 0.0001$) and at 4 months ($r = 0.97$, $p < 0.0001$). Hence, DAS28-CRP(3) and DAS28-CRP(4) agree well on group level that are relevant for analysis of group-level data in a clinical trial setting (Madsen 2011).

A sensitivity analysis will also be performed using the 4 components DAS28-hsCRP on these subjects. The clinical team will determine on a subject by subject basis how the subject's global assessment of disease activity VAS in the DAS28-hsCRP from each subject was scored, and identify subjects who consistently completed the subject's global assessment of disease activity reverse VAS scale to include in this analysis. Only subjects who completed this VAS scale in a consistent manner throughout the study will be included in this analysis; other subjects will be excluded. For subjects who will be included in this analysis using the reversed scale, the values collected will be changed using 100 minus the original value to determine the final score to be used in the analysis. The details of the subjects who will be included for this sensitivity analysis will be provided in a separate document.

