7.7.4 Analysis of Secondary Endpoints

For secondary endpoints, change from baseline will be analyzed at Weeks 2, 4, 8, and 12 using a mixed model repeated measures (MMRM) analysis. The Chi-square tests will be used to compare the ACR20, ACR50, and ACR70 rates between the active treatment and placebo groups at Weeks 2, 4, 8, and 12. The median hsCRP will be summarized descriptively.

The DAS28-related secondary endpoint is based on 3 individual components including TJC, SJC and hsCRP (see calculation in Appendix 13.6). Sensitivity analyses based on the 4-component DAS28-hsCRP (consisting of 4 individual components including TJC, SJC, hsCRP, and subject's global assessment of disease activity [VAS]; see calculation in Appendix 13.6) will be performed using the ITT set restricted to subjects who consistently completed the subject's global assessment of disease activity reverse VAS scale.

All secondary endpoints will be analyzed using the ITT and PP analysis sets. The ACR20, ACR50, and ACR70 will be also analyzed using the mITT set, where results for subjects that are missing at the relevant visit will be imputed using nonresponder imputation (NRI).

For analyses on ACR responses (ACR20, ACR50 and ACR70) described above, the analysis will be performed on the subjects assessment of arthritis pain and physician global assessment of disease activity VAS scales, using the same approach as the sensitivity analysis on 4-component DAS28-hsCRP to identify the subjects to be included in this analysis set.

For the analyses on the other VAS-related secondary endpoints (ie, the individual assessments using VAS), using the same approach as the sensitivity analysis on 4-component DAS28-hsCRP, only subjects who completed the corresponding individual VAS assessment consistently will be included.

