8.2.5. Sensitivity Analysis: Using 4-component DAS28-hsCRP

Repeat the statistical analysis (described in [Section 8.2.1](#)) on the ITT set using 4-component DAS28-hsCRP as calculated in [Section 8.1.1](#). Only subjects who completed the subject global assessment of disease activity consistently will be included in this sensitivity analysis.

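### SAP 8.1.5 subtracts every global VAS value from 100 without condition, so any original-anchor subject whom the SAP wording admits would be scored backwards

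*SAP*

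**What the plan says.** **Scoring.** SAP 8.1.5 describes one form for both global scales, "where the left end (0 mm) represents not well and the right end (100 mm) represents very well". It first defines the analysis score by an anchor: it "will be the length from the anchor of very well to the vertical tick marked by the physician and subject". The same sentence then turns this definition into a formula, "namely the value of 100 minus the number reported on eCRF page". No condition on the form used is attached. For pain, SAP 8.1.4 takes the length from the no-pain anchor, "which is the number reported on eCRF using the correct scale and the value of 100 minus the number reported using the reversed scale".

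**Which anchors were used.** Protocol 6.3.1 says of the subject global VAS that "some sites used the reverse scales, while others used the original anchors". SAP 8.1.5 says, for the physician and subject globals together, only that scoring varied across sites.

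**When the protocol subtracts from 100.** Protocol 6.3.1 applies the step to subjects "included in this analysis using the reversed scale, the values collected will be changed using 100 minus the original value".

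**Who is analysed.** Protocol 6.3.1, 7.7.3 and 7.7.4 restrict the 4-component DAS28-hsCRP analysis to subjects who consistently used the reverse scale. Protocol 7.7.4 extends that approach to the ACR responses and to the individual VAS endpoints, where "only subjects who completed the corresponding individual VAS assessment consistently will be included". SAP 8.2.5 says: "Only subjects who completed the subject global assessment of disease activity consistently will be included in this sensitivity analysis". SAP 8.1.5 leaves the list of subjects to a separate document that the sponsor finalises before database lock.

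**The concern.** One fixed formula cannot be right for two opposite orientations. On the reversed form, 100 minus the recorded value gives the distance from the *very well* end. On the original anchors the recorded value is already that distance, and subtracting it from 100 turns improvement into worsening.

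The protocol avoids this in two ways: it limits the analysed subjects to reverse-scale users, and it makes the subtraction conditional. The SAP keeps neither safeguard explicitly. Section 14 of the SAP declares no changes to the planned analysis, so the loss of the word *reverse* is not a disclosed decision.

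At stake are the subject global secondary endpoint, possibly the physician global endpoint, at most two of the five ACR items, and the 4-component DAS28-hsCRP sensitivity analysis. The baseline VAS summaries in SAP 6.2 could also be affected.

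**Working it through.** The plan states no figure on this point, so there is none to reproduce. The check is one of direction, then of wording, then of size.

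**Inputs.** SAP 8.1.5: score = 100 − recorded value. SAP 8.1.1: PtGA enters DAS28-hsCRP(4) at 0.014 per mm, with 0 = very well and 100 = not well. SAP 8.1.2: an ACR response needs at least 3 of 5 items, two of which are the global scales. Assumed, because the documents give no values: a subject whose true distance from *very well* falls from 70 to 40 mm, and a true arm difference of 10 mm.

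**Step 1: direction.**

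| Form used | Recorded | After 100 − value | Change |
|---|---|---|---|
| Reversed | 30 → 60 | 70 → 40 | −30 (correct) |
| Original anchors | 70 → 40 | 30 → 60 | +30 (inverted) |

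For the original-anchor subject:
- Percent improvement, taken as the fall divided by baseline, goes from 30/70 = 42.9% to −30/30 = −100%.
- The DAS28-hsCRP(4) contribution goes from 0.014 × (−30) = −0.42 to +0.42, an error of 0.84 for that one subject.
- If both global scales were inverted, a truly improving subject would lose two ACR items and would need all three of pain, HAQ-DI and hsCRP.

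The result also breaks the definition in SAP 8.1.5. The length from the *very well* anchor is 70 then 40 on either form.

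**Step 2: who can be analysed.**

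| Analysis | Protocol | SAP |
|---|---|---|
| DAS28-hsCRP(4) | Consistent users of the reverse scale (6.3.1, 7.7.3, 7.7.4) | Consistent users, direction not named (8.2.5, 8.3.2) |
| ACR responses | Same approach as DAS28-hsCRP(4) (7.7.4) | Consistent on both globals and pain, direction not named (8.3.1, 8.3.2) |
| Individual VAS endpoints | Same approach, consistent completers (7.7.4) | Completers; the consistency condition is missing in 8.3.1 but present for subgroups in 8.5 |
| Baseline VAS summaries | Not addressed | No restriction (6.2) |

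On the SAP column alone, a subject who used the original anchors at every visit is a consistent completer and qualifies.

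**Step 3: size at group level.** Suppose a share q of the analysed subjects in each arm is inverted, and the true arm difference D is the same in inverted and other subjects. The observed difference in mean change is (1 − q)D − qD = D(1 − 2q). The loss in DAS28-hsCRP(4) is 0.014 × 2qD. With D = 10 mm:

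| q (assumed) | VAS difference read | DAS28-hsCRP(4) lost |
|---|---|---|
| 10% | 8 mm | 0.028 |
| 20% | 6 mm | 0.056 |
| 30% | 4 mm | 0.084 |

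If the list follows the protocol, q = 0 and nothing is lost.

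**The case against.** The strongest reply is that the documents, read together, admit only reverse-scale users. Protocol 7.7.4 does say only *consistently* for the individual VAS endpoints, but the same sentence refers back to the approach used for DAS28-hsCRP(4), and that approach names the reverse scale. SAP 8.3.1 uses the same back-reference for ACR, and 8.5 repeats it for subgroups. With section 14 declaring no changes, the missing word may be mere abbreviation. For reverse-scale users the subtraction is correct.

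The contrast with pain is also weaker than it looks. SAP 8.1.4 describes two pain forms across protocol versions and an eCRF page that records the switch. SAP 8.1.5 describes a single global form, which one formula fits. The definition as a length from the *very well* anchor is safe in either direction.

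Most of this stands as a limit on what can be claimed, and it rules out the reading that such subjects certainly are scored backwards. It does not repair the rule. The back-references in the SAP lead to 8.2.5, which does not name a direction. The explicit formula contradicts the definition beside it for any original-anchor form. The baseline summaries in 6.2 carry no restriction. A programmer working from the SAP has no instruction to leave an original-anchor value alone.

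**Conclusion.** The scoring rule in SAP 8.1.5 is wrong as written: it gives an inverted score for any original-anchor subject it reaches, and the SAP's inclusion wording allows such subjects in. Confidence is moderate, because the harm depends on a list that is not in the documents.

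Four stronger conclusions are not supported:

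- *That subjects are in fact inverted.* The share q is not given, and it is 0 if the protocol restriction is applied.
- *That the physician global is inverted too.* Original anchors are documented only for the subject global. For the physician global the SAP says only that scoring varied.
- *That the error rivals the design difference.* The 0.84 is one subject's error under an assumed 30 mm improvement. The 0.80 in SAP 4.3 is a difference between group means. The comparable group-level loss is 0.03 to 0.08 for q from 10% to 30% and an assumed 10 mm difference, with equal q and equal true effects in the arms.
- *That the main result is at risk.* The primary endpoint, DAS28-hsCRP(3), contains no VAS component. In ACR at most two of five items are affected, and in DAS28-hsCRP(4) one of four components.

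**What to change.** In SAP 8.1.5, use the form of rule in 8.1.4: 100 minus the reported value only where the reversed scale is documented, otherwise the reported value. Record the direction per subject and per scale (subject global, physician global) in the pre-lock VAS document, so that the second branch applies only where the original anchors are established. This scores correctly whichever subjects are listed, and it also serves the baseline summaries in 6.2.

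For DAS28-hsCRP(4), restore *reverse* in SAP 8.2.5 and 8.3.2 to match the protocol, or declare the wider inclusion as a departure in section 14. Add the missing consistency condition for the individual VAS endpoints in 8.3.1.

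The cost is one rewritten sentence, a few restored words, and one flag in a list that is already being prepared before lock. No new data collection is proposed.

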8.1.6. Health Assessment Questionnaire-Disability Index (HAQ-DI)

The HAQ-DI is a subject-reported questionnaire that is commonly used to measure the disease associated disability. It consists of 8 sections which are dressing or grooming, arising, eating, walking, hygiene, reach, grip, and activities.

The disability section of the questionnaire scores the subject's self-perception on the degree of difficulty (0 = without any difficulty, 1 = with some difficulty, 2 = with much difficulty, and 3 = unable to do). The reported use of special aids or devices and/or the need for assistance of another person to perform these activities is also assessed. For each section, the score will be the worst score within that section. In addition, if an aide or device is used or if help is required from another individual, the minimum score for that section is 2. If the section score is 2 or more then no modification is made. The scores for each of the functional sections will be averaged to calculate the functional disability index. The disability index will be considered as missing when the subject does not have scores for at least 6 sections.

Full detail of algorithm to score HAQ-DI can be found in protocol Appendix 13.10.

8.1.7. hsCRP

hsCRP will be evaluated in the central laboratory. If due to COVID-19 pandemic, the central laboratory analysis cannot be performed (like the samples cannot be shipped to the central laboratory) and the samples are analyzed locally instead, then the local laboratory results will be included in the primary analyses/summaries.

8.2. Primary Efficacy Endpoint

The primary efficacy endpoint is the mean change from baseline in DAS28-hsCRP at Week 12, which is based on three individual components including TJC28, SJC28 and hsCRP (see calculation in [Section 8.1.1](#))

8.2.1. Primary Analysis

The primary analysis will be conducted on observed cases, which means DAS28-hsCRP at Week 12 will be calculated only when all the three individual components (TJC28, SJC28 and hsCRP) are assessed at this visit; otherwise, DAS28-hsCRP at Week 12 will be considered as missing.

The change from baseline in DAS28-hsCRP at visit Week 12 will be analyzed using an analysis of covariance (ANCOVA) model. The model will include treatment groups as a factor and DAS28-hsCRP at baseline as a covariate. Within-group least-square (LS) means and the associated standard errors (SE), the treatment differences in LS means and the associated SEs, the 2-sided 95% CIs, the 2-sided p-values for treatment comparisons between each of active treatment group and placebo group, and the 2-sided p-values for treatment comparisons among active treatment groups (high dose vs. low dose) will be estimated and provided. Descriptive statistics of baseline, observed value and change from baseline at Week 12 will be summarized by treatment group.

The primary efficacy analyses will be performed based on the ITT set, and then repeated using the PP set.

